ULN	Upper limit of normal
WHO	World health organisation

1 STUDY DETAILS

This statistical analysis plan (SAP) contains a more detailed description of the analyses in the clinical study protocol (CSP). This SAP is based on version 3.0 of the CSP.

1.1 Study Objectives

The study objectives and the corresponding endpoints/variables are shown in Table 1.

Table 1 Study objectives and corresponding endpoints/variables

Primary objective:	Primary endpoints/variables:
To assess the ORR of savolitinib in combination with osimertinib versus savolitinib in combination with placebo in patients with EGFRm+, MET amplified locally advanced or metastatic NSCLC who have progressed on previous osimertinib therapy.	Objective response rate is defined as the proportion of patients with measurable disease who have a CR or PR as determined by the investigator at the local site per RECIST 1.1.
Secondary objectives:	Secondary endpoints/variables:
To determine the efficacy of savolitinib in combination with osimertinib versus savolitinib in combination with placebo in patients with EGFRm+, MET amplified locally advanced or metastatic NSCLC who have progressed on previous osimertinib therapy.	
 • Progression-free survival is defined as time from randomisation until progression per RECIST 1.1 as assessed by the investigator or death due to any cause. • Duration of response is defined as the time from the date of first documented response until date of documented progression per RECIST 1.1 as assessed by the investigator or death in the absence of disease progression. • Tumour size assessment is defined as the percentage change from baseline in TLs at 12 weeks per RECIST 1.1 as assessed by the investigator. • Overall survival is defined as time from randomisation until the date of death due to any cause.


To evaluate the efficacy of savolitinib plus osimertinib in patients who cross-over after progression on savolitinib plus placebo. ^a
	
 • Objective response rate is defined as the proportion of patients with measurable disease who have a CR or PR as determined by the investigator at the local site per RECIST 1.1. • Progression-free survival is defined as time from the first dose in the cross-over period until progression per RECIST 1.1 as assessed by the investigator or death due to any cause. • Duration of response is defined as the time from the date of first documented response during the cross-over period until date of documented progression per RECIST 1.1 as assessed by the investigator or death in the absence of disease progression. • Tumour size assessment is defined as the percentage change from baseline in TLs at 12 weeks per RECIST 1.1 as assessed by the investigator.

To evaluate the PK of savolitinib and osimertinib.
	
Plasma concentrations of savolitinib, osimertinib, and their metabolites.

To determine the prevalence of ctDNA clearance after savolitinib plus osimertinib or savolitinib plus placebo treatment in this patient population.
	
Total clearance in EGFR mutations at 6-weeks after therapy initiation (percentage and absolute change from baseline in EGFR mutation allele frequencies).

Safety objective:
	
Safety endpoints/variables:

To evaluate the safety and tolerability of savolitinib plus osimertinib or savolitinib plus placebo.
	
Safety and tolerability will be evaluated in terms of AEs, SAEs and discontinuation rate due to AEs. Clinical chemistry/haematology including LFTs, ECHOs, ECGs and vital signs including blood pressure and heart rate.

Tertiary/exploratory objectives:
	
Tertiary/exploratory endpoints/variables:

^a Baseline for ORR, PFS, DoR and tumour size assessments of patients who cross-over to savolitinib plus osimertinib from savolitinib plus placebo will be the progression scan on savolitinib plus placebo acquired within 28 days of the start of treatment in the cross-over period.

CCI

1.2 Study Design

This is a multi-centre, Phase II, double-blind, randomised study designed to determine the efficacy of savolitinib administered orally in combination with osimertinib versus savolitinib in combination with placebo in patients with EGFRm+, MET amplified, locally advanced or metastatic NSCLC who have progressed on previous osimertinib treatment.

Prior to CSP Version 3.0, approximately 56 patients were planned to be randomised in a ratio of 1:1 to receive treatment with CCI savolitinib once daily plus CCI osimertinib once daily, or CCI savolitinib once daily plus placebo. At least half of the patients randomised into the study will be second line patients who were treated with osimertinib as first line therapy. Randomisation will be stratified according to the number of prior lines of therapy (i.e., osimertinib monotherapy as first line or \geq second line [which includes patients who received osimertinib monotherapy before or after chemotherapy]).

Prospective testing of tumour specimens to determine MET amplification by central fluorescence in situ hybridisation (FISH) using tumour specimens collected after progression on prior treatment with osimertinib should be performed at Pre-screening in advance of Screening. Patients determined to be MET amplified in Pre-screening will undergo screening during the 28 days prior to randomisation to confirm eligibility.

All patients confirmed as eligible will begin treatment on Day 1 with savolitinib plus osimertinib or savolitinib plus placebo. Treatment will continue once daily in 28-day cycles until either

objective PD by RECIST 1.1 is assessed, unacceptable toxicity occurs, consent is withdrawn, or another discontinuation criterion is met. Patients randomised to the savolitinib plus placebo arm may cross-over to open-label savolitinib plus osimertinib following investigator-assessed objective PD to ensure that all patients enrolled may have the opportunity to receive the combination of savolitinib plus osimertinib.

A non-comparative interim futility analysis for the savolitinib plus placebo arm was planned to occur after 20 patients overall (10 per arm) had the opportunity of being treated for 2 RECIST post-baseline scans (12 weeks). Recruitment was to continue during this interim futility analysis.

[figure not shown]
Randomised study design, cross-over study design and end of study design are described in the CSP Section 4.1.

Under CSP V3.0, as a result of AstraZeneca's decision to terminate study recruitment early, the planned interim futility analysis and primary analysis will not be performed, and there will be no requirement for data review by the IDMC. Alternatively, an initial data cut-off (DCO) will occur following the early termination of study recruitment to allow an early review of the data by AstraZeneca. The study will be unblinded after completion of data cleaning activities on the initial DCO data, and patients on savolitinib monotherapy (savolitinib plus placebo) will be given the opportunity to cross-over to the savolitinib plus osimertinib arm after approval by AstraZeneca.

If it is decided that a patient will switch to savolitinib plus osimertinib before final database lock, then they will follow the scheduled procedures described in CSP Table 2. Patients may otherwise choose to remain on savolitinib monotherapy (as long as, in the opinion of the investigator, they are still receiving clinical benefit and have not reported PD). All patients will be followed until the final DCO for the final analysis, which will occur after all randomised patients have had a 9-month follow-up. CCI

For an overview of the study design see [Figure 1](#).

Figure 1 Study Design

EGFRm+ = Epidermal growth factor receptor mutation positive; MET = Hepatocyte growth factor receptor; NSCLC = Non-small cell lung cancer.

1.3 Number of patients

Prior to CSP V3.0, the treatment of approximately 56 patients (28 per arm) with EGFRm+ and MET amplified locally advanced or metastatic NSCLC who have progressed following treatment with osimertinib was considered adequate for this study. CCI

At least half of the patients planned to be randomised into the study will be second-line patients who were treated with osimertinib as first-line therapy.

Under CSP V3.0, the planned number of randomised patients will not be met. This is a result of the decision by AstraZeneca to terminate study recruitment early.

2 ANALYSIS SETS

2.1 Definition of Analysis Sets

Patients will be assigned to the following analysis sets prior to any analyses being performed.

Full Analysis Set (FAS)

The FAS will include all randomised patients with treatment groups assigned in accordance with the randomisation, regardless of the treatment actually received. Patients who were randomised but did not subsequently receive treatment are included in the FAS. The analysis of data using the FAS therefore follows the principles of intention to treat.

The FAS will be the primary population for reporting efficacy data and to summarise baseline characteristics.

Safety analysis set (SAF)

The Safety analysis set will consist of all randomised patients who received any amount of study treatment. Safety data will not be formally analysed but summarised using the safety analysis set according to the treatment received. If a patient receives any amount of an experimental therapy, they will be summarised in the treatment group corresponding to the first experimental treatment they received.

Cross-over analysis set

The Cross-over analysis set will consist of all patients who were randomised to savolitinib in combination with placebo and received at least one dose of savolitinib plus osimertinib in the cross-over period of the study.

It will be used as the population for reporting the efficacy and safety data for patients who crossed over to treatment with savolitinib plus osimertinib following objective progression on savolitinib plus placebo.

PK analysis set

All patients who receive at least one dose of savolitinib or osimertinib as per the protocol, for whom there are at least one reportable PK concentration without any protocol deviation impacting PK, will be included in the PK analysis set. If a patient receives any amount of an experimental therapy, they will be summarised in the treatment group corresponding to the first experimental treatment they received.

Monotherapy analysis set

Under CSP V3.0, the Interim futility analysis set will no longer be required, since the planned interim futility analysis will not be performed. Prior to CSP V3.0, it would have included the first 20 enrolled patients (10 per arm) who had the opportunity to be treated for 2 RECIST post-baseline scans (12 weeks). Therefore, a Monotherapy analysis set is defined including the first 10 randomised patients from the savolitinib plus placebo arm only, to be selected after any randomised patients who were accidentally unblinded are first excluded.

Details of the analysis sets are presented in [Table 2](#).

Table 2 Summary of outcome variables and analysis sets

Outcome variable	Analysis set	Summarised by biomarker groups^a
Efficacy data		
ORR, PFS, DoR, OS	FAS	Yes
Change in tumour size	FAS	Yes
Study Population/Demography Data		

Table 2 Summary of outcome variables and analysis sets

Outcome variable	Analysis set	Summarised by biomarker groups^a
Demography characteristics (e.g. age, sex etc.)	FAS	Yes
Baseline and disease characteristics	FAS	Yes
Important deviations	FAS	Yes
Medical/surgical history	FAS	Yes
Previous anti-cancer therapy	FAS	Yes
Concomitant medications/procedures	FAS	Yes
Subsequent anti-cancer therapy	FAS	Yes
PK Data		
PK data	PK	No
Monotherapy analysis		
ORR	Monotherapy	No
Safety data		
Exposure	Safety	Yes
Adverse events	Safety	No
Laboratory measurements	Safety	No
Vital signs	Safety	No
ECGs	Safety	No
ctDNA data	Safety	No
Cross-over analysis		
Baseline characteristics	Cross-over analysis set	No
Efficacy endpoints	Cross-over analysis set	No
Safety data	Cross-over analysis set	No

^aBiomarker groups are defined as subsets of randomised patients who are FISH10+, CCI, and FISH10+ and/or CCI, as described in Section 3.5.

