3 PRIMARY AND SECONDARY VARIABLES

3.1 Derivation of RECIST Visit Responses

For all patients, the RECIST tumour response data will be used to determine each patient's visit response according to RECIST version 1.1. It will also be used to determine if and when a patient has progressed in accordance with RECIST and their best objective response to study treatment.

Baseline radiological tumour assessments are to be performed no more than 28 days before the start of randomised treatment and ideally as close as possible to the start of study treatment.

For patients who cross-over to savolitinib plus osimertinib based on confirmed objective disease progression during the initial randomised treatment period (including patients who have already crossed over based on confirmed PD prior to CSP V3.0) the baseline scan for response endpoints during the cross-over period will be the progression scan on savolitinib plus placebo, which should be acquired within 28 days of the start of treatment in the cross-over period. Scheduled RECIST 1.1 tumour assessments are not required for these patients, and the subsequent assessment of disease progression will be based on standard-of-care scan or investigator determined clinical progression.

For patients who cross-over after study unblinding and who have not objectively progressed during the initial randomised treatment period, scheduled RECIST 1.1 tumour assessments are

required using initial randomisation as baseline. Patients who then discontinue study intervention after cross-over for reasons other than investigator-confirmed disease progression will continue scheduled RECIST 1.1 tumour assessments until objective disease progression per RECIST 1.1 as assessed by investigator, unless they withdraw consent to the entire study. These tumour assessments are then performed every 6 weeks following the start of study treatment up to 24 weeks relative to initial randomisation, then every 8 weeks until objective disease progression.

If an unscheduled assessment is performed, and the patient has not progressed, every attempt should be made to perform the subsequent assessments at their scheduled visits. This schedule is to be followed in order to minimise any unintentional bias caused by some patients being assessed at a different frequency than other patients.

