3.2 Efficacy Variables

3.2.1 Objective response rate (ORR)

ORR is defined as the percentage of patients with at least one investigator-assessed visit response of CR or PR and will be based on a subset of all randomised patients with measurable disease at baseline per the site investigator. ORR will also be defined using the BICR data to

define a visit response of CR or PR, with the denominator defined as subset of all randomised patients with measurable disease at baseline per BICR.

Data obtained up until progression, or last evaluable assessment in the absence of progression, will be included in the assessment of ORR. Patients who discontinue randomised treatment without progression, receive a subsequent anti-cancer therapy (note that for this analysis radiotherapy is not considered a subsequent anti-cancer therapy) and then respond will not be included as responders in the ORR.

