4.2.2 Primary Efficacy Endpoint

4.2.2.1 Objective response rate (ORR)

The ORR will be based on the site investigator RECIST data, and using all scans regardless of whether they were scheduled or not. The ORR will be summarised by n (%) in each treatment arm.

Summaries by treatment group will be produced that present the number and percentage of patients with a tumour response (CR/PR) based upon the number of patients with measurable disease at baseline per the site investigator. The response rates by treatment group will be presented with a 2-sided 95% CI using the Clopper-Pearson method.

This analysis of ORR will be repeated for second line patients (i.e. patients with one prior line of therapy before the study treatment).

These summaries will also be produced for ORR per BICR (based upon the number of patients with measurable disease at baseline per BICR). If there is an important discrepancy between the primary analysis using the site investigator data and this sensitivity analysis using BICR data then the proportion of patients with site but no central confirmation of progression will be

summarised; such patients have the potential to induce bias in the central review due to informative censoring. Disagreements between investigator and central reviews of RECIST progression will be presented for each treatment group.

Additionally, a summary of ORR in the first 10 monotherapy arm patients who have had the opportunity to be treated for two RECIST post-baseline scans (12 weeks, the Monotherapy Analysis Set) will be performed. This summary will have no impact on the CoC study and will only be used for exploratory purposes. The first 10 randomised patients will be selected from the savolitinib plus placebo arm, after first excluding any randomised patients who were accidentally unblinded.

For each treatment group best objective response (BoR) will be summarised by n (%) for each category (CR, PR, SD, PD and NE) based upon the FAS. This analysis will be repeated for second line patients (i.e. patients with one prior line of therapy before the study treatment).

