4.2.4 Data cut-offs

The data cut-off for futility analysis was planned to take place after 20 patients overall (10 per arm) have had the opportunity to be treated for 2 RECIST post-baseline scans (12 weeks). In order to ensure that 10 patients in the savolitinib plus placebo group have been randomised for inclusion into the futility analysis set, the IWRS was to be used to determine when 22 patients have been randomised into the study.

The data cut-off for primary analysis was planned to take place 6 months after last subject in (LSI). The data cut-off for final analysis was planned to take place at the earlier of 18 months after LSI or when 70% of patients have progressed or died.

Under CSP v3.0, an initial DCO will occur to allow an early review of data by AstraZeneca. A final DCO will occur 9 months after the last patient has been randomised, after which the final analysis will be performed. CCI These changes are a result of the decision by AstraZeneca to terminate study recruitment early.

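### Cross-over ORR and BoR require no minimum scan opportunity before the fixed final cut-off, so late cross-overs enter the denominator as non-responders because of the calendar

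*SAP*

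**What the plan says.** **Who is in the set.** SAP Section 2.1 admits placebo-arm patients who "received at least one dose of savolitinib plus osimertinib in the cross-over period of the study". It then describes the set as reporting patients who crossed over "following objective progression on savolitinib plus placebo", which is narrower than the membership rule. Table 2 assigns the cross-over efficacy endpoints to this set.

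**When patients can cross over.** Section 1.2 allows cross-over after investigator-assessed progression. Under CSP V3.0 it also allows cross-over without progression, once the study is unblinded and the sponsor approves. It sets out the procedures that apply in this case: "If it is decided that a patient will switch to savolitinib plus osimertinib before final database lock".

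**When data stop.** Section 4.2.4: "A final DCO will occur 9 months after the last patient has been randomised".

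**How response is counted.** Table 1 defines the cross-over endpoint: "Objective response rate is defined as the proportion of patients with measurable disease who have a CR or PR". Section 3.2.1 gives the responder rule: "ORR is defined as the percentage of patients with at least one investigator-assessed visit response of CR or PR". Neither requires a scan after cross-over. Section 3.2.5 gives BoR the same denominator as ORR.

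**Scans after cross-over (Section 3.1).** For cross-over on progression, the progression scan is the baseline and "Scheduled RECIST 1.1 tumour assessments are not required for these patients". For cross-over without progression, the baseline is initial randomisation. Scans run 6-weekly to week 24 from randomisation and 8-weekly after that.

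**An opportunity condition elsewhere.** Section 4.2.2.1 describes the monotherapy ORR as covering the first 10 patients "who have had the opportunity to be treated for two RECIST post-baseline scans (12 weeks, the Monotherapy Analysis Set".

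**The concern.** A response rate can be interpreted only if each patient in the denominator had a fair chance to show a response. In the randomised comparison the 9-month rule gives that chance, because the clock runs from randomisation. After cross-over nothing plays that role: the clock runs from cross-over, one dose is enough to enter, and the cut-off ignores the cross-over date.

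A patient who starts the combination a few weeks before the DCO may have no scan by then, yet adds one to the denominator and nothing to the numerator. Efficacy after cross-over is a stated secondary objective. The set can only be a part of one arm of a trial that stopped recruiting early, so a few such patients could shift the estimate visibly.

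**Working it through.** The SAP gives no size, expected rate or cross-over dates for this set, so there is no planned figure to reproduce.

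**1. Time left after a late cross-over.** Nine months is 9 × 30.4375 / 7 = 39.1 weeks. For the last patient randomised, the latest cross-over week that leaves a given time before the DCO is:

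| Time needed after cross-over | Latest cross-over, weeks from randomisation |
|---|---|
| 6 weeks | 39.1 − 6 = 33.1 |
| 8 weeks | 39.1 − 8 = 31.1 |
| 12 weeks | 39.1 − 12 = 27.1 |
| 13 weeks (12 + 1-week window) | 39.1 − 13 = 26.1 |

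Patients randomised earlier have longer from randomisation to DCO, but their time after cross-over is no better protected.

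**2. The two routes differ.**
- *Without progression:* scans stay on the randomisation schedule. After week 24 they fall at 24 + 8 = 32 and 32 + 8 = 40 weeks. For the last patient randomised, week 40 lies just beyond 39.1. A cross-over after the week 32 scan then has no scheduled scan before the DCO, unless the next one is done at the very start of its ±1-week window (week 39).
- *On progression:* no RECIST scans are scheduled. Whether a scan exists depends on standard of care, so response data can be absent however early the patient crosses over. A late cross-over adds to that.

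**3. Dilution.** Let p be the ORR if everyone had an opportunity, and f the share of the denominator without one. If those patients have the same underlying rate but cannot record a response, expected observed ORR = p × (1 − f). All p and f below are assumptions.

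| p | f = 10% | f = 20% | f = 30% | f = 40% |
|---|---|---|---|---|
| 20% | 18% | 16% | 14% | 12% |
| 30% | 27% | 24% | 21% | 18% |
| 40% | 36% | 32% | 28% | 24% |
| 50% | 45% | 40% | 35% | 30% |

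**4. An illustration in counts (assumed).** Ten patients cross over, two without time for a scan, and four respond. The SAP's rule gives 4/10 = 40.0% (Clopper-Pearson 95% CI 12.2 to 73.8). Among those with an opportunity it is 4/8 = 50.0% (15.7 to 84.3).

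**5. Week 12 tumour size.** Section 3.2.6 needs a week 12 measurement or an earlier progression scan. The only week 12 imputation it describes is scaling when at most one-third of target lesions are missing because of intervention. The +20% value belongs to best percentage change, in listed death and progression situations. A patient with no scan therefore drops out of the week 12 summary.

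**The case against.** The strongest reply is that this is a descriptive summary with discretion already built in. Section 4.2.10 repeats only selected analyses, where the data suffice, and Section 4.2.1 plans no inference. That limits the consequences. But the caveat decides whether an analysis is run; it does not say which patients belong in the denominator.

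Four stronger readings are tempting and are not supported:

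- *That cross-over is open until database lock.* A reader might infer this from Section 1.2, but the sentence says which procedures apply to a switch before lock and does not define an entry window. The final-DCO statements are also followed by redactions, so the handling of first doses after the DCO cannot be judged from this copy. The point does not need this reading: a cross-over shortly before the DCO is enough.
- *That unscanned patients also count as failures for week 12 tumour size.* They are missing, as shown above.
- *That the bias is always towards zero.* Patients who cross over without progression keep the randomisation baseline, and the SAP does not say whether a response before cross-over counts. If it does, some count as responders without any post-cross-over effect, so the direction is uncertain for them.
- *That the cross-over ORR will be compared with the randomised combination arm.* No such comparison is planned.

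It is also fair to say that the 12-week condition appears only in Section 4.2.2.1; the definition of the Monotherapy set in Section 2.1 does not repeat it. A hard restriction here would discard observed responses from a small set. Both points argue for a companion analysis, not a replacement.

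**Conclusion.** The point stands for cross-over ORR and BoR. One-dose entry, a DCO unrelated to the cross-over date and no scan-opportunity condition together let patients count as non-responders without having been assessed. The expected loss is a factor of (1 − f): from an assumed 40% down to 36% at f = 10% and 24% at f = 40%. This assumes that patients without an opportunity cannot record a response and would otherwise respond at the same rate. The true f is unknown, and the effect is nil if nobody crosses over late.

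Late cross-over is not the only source of missing response data, because patients who cross over on progression have no scheduled RECIST scans. The primary endpoint is unaffected. This is worth correcting in a stated secondary objective, but it does not threaten the trial's main result.

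**What to change.** Add to Section 4.2.10:

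1. Report cross-over ORR and BoR in the full set as now. Beside it, report them in patients whose first cross-over dose precedes the final DCO by a stated minimum, for example 13 weeks (the 12 weeks used for the monotherapy ORR plus the 1-week window).
2. Give the number with no evaluable post-cross-over scan, separately for cross-over on progression and without progression, and the number missing from the week 12 tumour size summary.
3. State that for cross-over without progression only responses first documented after cross-over count, and give the number already in response at cross-over.
4. Keep the full set for safety, PFS and DoR; for PFS and DoR, censoring deals with short follow-up.

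The cost is a few sentences and one extra table. The rule uses calendar dates only, so it does not depend on outcome and can be fixed before database lock. The companion analysis has a smaller denominator and a wider interval, and does not by itself supply scans for patients who crossed over on progression. That is why the counts in item 2 are needed as well.
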